7. PRECISION BY SAMPLE SIZE

Table 1 summarises the margin of error at the 95% confidence level provided by varying sample sizes and estimates of percentage of physicians indicating a correct response. For example, if the estimate of the percentage of physicians indicating a correct response to an individual survey question is 60%, then a sample of 200 physicians will provide a margin of error of \pm 7.0 percentage points of this estimate with a 95% confidence interval.

Sample Size	Proportion of Correct Responses to Each Question							
	50	60	70	75	80	85	90	
	Precision/ Margin of Error (±%) with 95% Confidence Interval							
50	14	14	12	11	10	9.0	8.0	
100	10	10	9.0	8.0	8.0	7.0	6.0	
150	8.0	8.0	7.3	7.0	6.7	5.7	4.7	
200	7.0	7.0	6.5	6.0	5.5	5.0	4.0	
250	6.0	6.0	5.6	5.4	4.8	4.6	3.6	
300	5.7	5.7	5.3	5.0	4.7	4.0	3.3	
350	5.1	5.1	4.9	4.4	4.3	3.9	3.1	
400	5.0	4.8	4.5	4.3	4.0	3.5	3.0	
450	4.7	4.4	4.2	3.9	3.8	3.2	2.7	
500	4.4	4.2	4.0	3.8	3.6	3.2	2.6	

Table 1 Sample size and precision estimates

8. STUDY LIMITATIONS

There are some limitations inherent in the study design.

The sample of the physicians who are invited to participate will be a random sample of all physicians who received a DHCP letter. The sample of participating physicians will be self-selected since respondents will voluntarily respond to the invitation to participate; however, the survey recruitment strategies are intended to recruit a heterogeneous sample of prescribers for participation.

A non-responder analysis will not be possible, so it will remain unknown, if there are TROBALT prescribers among the non-responders and what their understanding is of the risks.

In case of a very low response, known prescribers will be specifically invited to participate. Such enrichment of the sample is not anticipated to bias the outcomes as the targeted physicians will also be DHCP recipients and will need to fulfil inclusion criteria.

There is a possibility that TROBALT is prescribed by physicians who were not included on the mailing list for a DHCP, however this is unlikely since the indication for

TROBALT is restricted to a specific patient population that is normally treated by physicians who are epilepsy specialists.

Due to the low numbers of TROBALT prescribers per country, the main analysis will combine all countries. It is acknowledged that there may be differences between countries. However, the safety information in each country specifies the risks with TROBALT.

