3.3.1. Screening Phase

The Screening Phase seeks to survey physicians to identify the proportion of physicians who have prescribed TROBALT and to summarize the type of medical specialty of those physicians with experience in prescribing TROBALT.

Up to 1000 physicians will be invited to take part, by selecting a random sample of prescribers of AEDs from those who were sent a DHCP letter. Assuming a recruitment failure of 60%, this will permit a target sample of 200 prescribers and 200 non-prescribers to be achieved.

The survey will be composed of multiple choice and close-ended questions. There will be no open-ended questions included.

The electronic data capture (EDC) system will be configured to allow those physicians identified by their responses to the survey in the Screening Phase (Part 1) to transition into the Assessment Phase (Part 2). The EDC system will allow the first 200 physicians who indicate they have prescribed TROBALT since July 2013 to continue to Part 2 and will also limit to 200 the number of non-prescribers who are asked to complete the additional questions in Part 2.

[figure not shown]

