3.3.2. Assessment Phase

[figure not shown]
The Assessment Phase is the main part of the Physician Survey. In addition to the TROBALT prescribers, the Assessment Phase will include up to 200 respondents from the Screening Phase who have not prescribed TROBALT in order to evaluate the general awareness to the risks associated with TROBALT. The Assessment Phase will evaluate each physician's understanding of specific risks associated with TROBALT use.

The outcome of this study is the proportion of the physicians/epilepsy specialists that correctly respond to individual survey questions. The proportion responding correctly will be tabulated separately for each item.

Physician demographic information will be collected in order to further characterise the respondent population. This will include country, type of medical practice, and number of patients with epilepsy treated. The country in which practice occurs will be collected at the beginning of the survey in order to ensure a sample of respondents from each included country.

At the conclusion of the online survey, the final computer screen will display a summary of the relevant sections from the country-specific Prescribing Information to allow the physician access to the full TROBALT label, to ensure they have a reminder and full understanding of the safety revisions that were implemented in 2013.

^{*} In case of a very low response, known prescribers will be specifically invited to participate. Such enrichment of the sample is not anticipated to bias the outcomes as the targeted physicians will also be DHCP recipients and will need to fulfil inclusion criteria.

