3.4. Study Population

3.4.1. Physicians Prescribing Anti-Epileptic Drugs

This survey aims to recruit a random sample of 1000 physicians prescribing AEDs and who have been sent a DHCP letter in Austria, Belgium, Bulgaria, France, Hong Kong, Italy, Norway, Poland, Slovakia, Spain, Switzerland and the United Kingdom.

The selected countries are the eight largest markets in the EU for TROBALT use based on estimated number of patients receiving TROBALT (the United Kingdom, Spain, France, Italy, Belgium, Slovakia, Poland and Austria). One additional EU country (Bulgaria) was selected upon the potential uncertainty related to reimbursement of an ophthalmology exam mandated by the TROBALT PI. Three non-EU countries (Hong Kong, Norway and Switzerland) were selected to represent markets where TROBALT is available, outside the EU.

If required, additional countries may be included in the survey to reach the minimum recruitment target. The recruitment will be from among those who have prescribed an anti-epileptic drug at least once in the last 6 months, and who were on the list to which a DHCP letter was distributed in June 2013. The survey will aim to recruit at least 200 physicians (from the 12 specified countries) prescribing TROBALT for sub-analyses, as these individuals would be expected to be more aware of the risks of TROBALT, and up to 200 physicians not prescribing TROBALT as a comparison.

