6.2. Analyses

The primary outcome is the proportion of physicians answering each question of the understanding of the risks associated with TROBALT correctly. Point estimates for the proportion with correct responses, and associated confidence intervals, will be calculated for each question about the risks of TROBALT. In the case of multiple choice questions, the number and proportion of physicians reporting each response will also be provided.

The proportion of correct answers to survey questions will be summarised overall, and separately for those physicians who have prescribed TROBALT.

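### If known TROBALT prescribers are added, the screening share and the overall proportion correct both rise; the protocol's reason for expecting no bias does not hold

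*Protocol*

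**What the plan says.** The contingency is in the footnote to Protocol Section 3.3.2 and again in Section 8: "In case of a very low response, known prescribers will be specifically invited to participate". Both places add the same reassurance, which in Section 8 reads "Such enrichment of the sample is not anticipated to bias the outcomes as the targeted physicians will also be DHCP recipients" and goes on to mention the inclusion criteria. Section 8 also says that the invited physicians "will be a random sample of all physicians who received a DHCP letter".

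Four other statements bear on this:

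- Section 3.4.1 wants at least 200 TROBALT prescribers, "as these individuals would be expected to be more aware of the risks of TROBALT".
- Section 3.3.1 says that the Screening Phase "seeks to survey physicians to identify the proportion of physicians who have prescribed TROBALT".
- Section 3.3.1 also limits the Assessment Phase to the first 200 prescribers and to 200 non-prescribers.
- Section 6.2 states: "The primary outcome is the proportion of physicians answering each question of the understanding of the risks associated with TROBALT correctly". Results are given overall and separately for prescribers. The protocol mentions no weighting.

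**The concern.** Receiving the letter and meeting the entry criteria are common to everyone invited, so they cannot offset selection on something else. Known prescribers are chosen because they prescribe. That is the characteristic whose frequency the Screening Phase is meant to estimate, and the one the protocol expects to predict correct answers. Section 8's reassurance therefore conflicts with Section 3.4.1, and counting the added physicians would defeat the screening aim in Section 3.3.1. Once enrichment starts, the invited group is also no longer a random sample of letter recipients.

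The Protocol Summary says that the results will inform whether additional measures are needed. An overall proportion correct that is pushed upward errs towards reassurance.

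**Working it through.** **The plan's own figures.** At n = 200 and 60% correct, the simple normal margin is 1.96 × √(0.6 × 0.4 / 200) = 6.8 points, and the exact (Clopper-Pearson) half-width is 7.0, which matches Section 7. Also 1000 × (1 − 0.60) = 400 = 200 + 200, as in Section 3.3.1. Neither figure is in dispute.

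**Inputs from the protocol.** The cap of 200 non-prescribers (Section 3.3.1); prescribers expected to be more aware, with no size given (Section 3.4.1); Table 1 margins at 60% correct of 5.7 (n = 300), 5.1 (n = 350) and 4.8 (n = 400).

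**Assumed inputs, not in the protocol.** 300 random respondents; 100 known prescribers added; a true prescriber share of 10% or 20%; a knowledge gap (prescribers minus non-prescribers) of 10, 20 or 30 points.

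**Step 1: screening share.** With R random respondents, P prescribers among them and a added, the observed share is (P + a) / (R + a).

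- True share 10%: (30 + 100) / 400 = 32.5%.
- True share 20%: (60 + 100) / 400 = 40.0%.

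This needs no assumption about knowledge.

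**Step 2: prescriber share in the Assessment Phase, with the cap.**

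| True share | Without enrichment | With enrichment | Difference |
|---|---|---|---|
| 10% | 30 / 230 = 13.0% | 130 / 330 = 39.4% | 26.4 points |
| 20% | 60 / 260 = 23.1% | 160 / 360 = 44.4% | 21.4 points |

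**Step 3: shift in the overall proportion correct due to enrichment alone** = difference in share × knowledge gap.

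| True share | Gap 10 | Gap 20 | Gap 30 |
|---|---|---|---|
| 10% (n = 330) | +2.6 | +5.3 | +7.9 |
| 20% (n = 360) | +2.1 | +4.3 | +6.4 |

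With a gap of zero the shift is zero. At 30 points it exceeds the Table 1 margin, at 20 points it is close to it, and at 10 points it is well below it.

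**Step 4: what the cap does by itself.** The cap moves the share from 10% to 13.0%, or from 20% to 23.1%. That is worth about 0.3 to 0.9 points over gaps of 10 to 30, and it is not counted in Step 3.

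**Step 5: a poorer response.** Suppose only 200 random respondents, with known prescribers added until there are 200 prescribers. At true shares of 10/20/30% the screening share reads 200/380 = 52.6%, 200/360 = 55.6% and 200/340 = 58.8%. With a 20-point gap the overall proportion correct rises by 8.5, 7.1 and 5.8 points. The cap does not bite here (180, 160 and 140 non-prescribers).

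**Step 6: within strata.** The proportion correct among prescribers does not depend on how many non-prescribers sit beside them, and the reverse is also true. The mix leaves both unchanged.

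**The case against.** Several points on the other side have force.

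- **Enrichment may never happen.** It depends on a very low response, which is not defined. This stands, and the point is conditional on it.
- **The overall figure is a quota blend anyway.** The 200/200 limits already move the mix away from the population, and enrichment brings the sample closer to the planned split. This stands as a description. It does not rescue the reassurance: the overall figure still changes with the number of known prescribers added, and no text says that it describes a 50:50 blend rather than letter recipients.
- **The stratum results carry much of the plan.** Section 6.1 defines two sub-populations and the Protocol Summary compares them. A reader might infer that enrichment also distorts the prescriber estimate. The documents do not support that: it would require prescribers known to the sponsor to differ in knowledge from other prescribers, and the protocol does not address this. It is a risk to check, not a demonstrated bias.
- **The no-bias sentence concerns outcomes.** Sections 4.2 and 6.2 define these as proportions correct. A reader might conclude that the protocol vouches for the screening share as well, but the text does not clearly say so. The screening share is distorted whether or not the sentence covers it.
- **Weighting or sensitivity tables could be in an SAP that is not shown.** Their absence is not the criticism. The criticism is that the protocol states, twice, a premise that would tell the analyst no such step is needed.

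**Conclusion.** The no-bias statement is wrong as written for the overall proportion correct, and enrichment would also spoil the screening share; both hold only if enrichment is used. Inflation of the screening share is certain if the added physicians are counted: 32.5% for 10%, or 40% for 20%, in the illustration. The overall proportion correct rises in any case where prescribers know more, as Section 3.4.1 expects. Enrichment alone adds 2.1 to 7.9 points in the illustration, against a Table 1 margin of about 5 to 6 points.

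The direction rests on the protocol's own text. The size rests on assumed shares, response counts and knowledge gaps. It would be too strong to say that the shift always exceeds the sampling margin, because with a gap of 10 points it does not.

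**What to change.** - Withdraw the no-bias sentence in the Section 3.3.2 footnote and in Section 8. Qualify Section 8's description of the invitees as a random sample in case enrichment occurs.
- Record the invitation source (random or enriched) with the unique code already planned in Sections 3.1 and 3.4.4, and carry it into the response data. This has to be set up before fielding, because Section 5 stores identifiers apart from responses.
- Estimate the Screening Phase share and the specialty summary from randomly invited physicians only.
- Present knowledge mainly by prescriber stratum. Take any overall figure from the random sample, or weight it to that sample's prescriber share as seen at screening. Weighting also removes the effect of the cap.
- Show the prescriber results with and without the enriched physicians as a sensitivity check.

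The cost is one field in the invitation file, one extra table column and a smaller n for random-only estimates. In the illustration at a 10% share, a random-only overall figure rests on 230 physicians rather than 330. Table 1 margins at 60% correct are then between 7.0 and 6.0 (n = 200 to 250) instead of between 5.7 and 5.1 (n = 300 to 350).

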9. STUDY MANAGEMENT

9.1. Ethical Committee Approval and Consent

Survey participation is voluntary. The survey will begin with a question indicating the physician's agreement to participate in the survey. If the individual does not agree, the survey will be ended.

Ethics approval will be sought as required by individual countries.

9.2. Reporting of Adverse Events

The reporting of Adverse Event (AE) is not expected or requested during the survey, because answers are closed-ended i.e., there are no free text fields into which the respondent could enter AE information. However, as reporting suspected adverse reactions after authorisation of the medicinal product is important to allow continued monitoring of the benefit/risk balance of the medicinal product, physicians will be asked to report any suspected AEs via the national reporting system.

9.3. Study Reporting and Publications

The recruitment period is estimated to be 6 months from March 2014, though this could be earlier if the target number of participants is reached sooner than September 2014. A final report will be written by Q4 2014 and uploaded in the EU PAS Register (www.encepp.eu).

10. APPENDICES

Appendix 1: Template for the letter to prescribers including the restrictions for use of TROBALT

Restrictions for use of Trobalt® (retigabine) - treatment may lead to pigment changes of ocular tissues, including retina, and skin, lips and/or nails

Dear Healthcare Professional

GlaxoSmithKline (GSK) would like to inform you of a restriction of the indication for Trobalt® (retigabine) following reports of pigment changes and provide you with recommendations for monitoring.

Summary

Trobalt® should now only be used as adjunctive treatment of drug-resistant partial onset seizures with or without secondary generalisation in patients aged 18 years or older with epilepsy, where other appropriate drug combinations have proved inadequate or have not been tolerated.

Pigment changes (discolouration) of ocular tissue, including the retina, have been reported in long-term clinical studies with retigabine.

Blue-grey discolouration of the nails, lips and/or skin have also been observed in these studies.

Patients currently receiving treatment should be reviewed at a routine (non-urgent) appointment. The balance of benefits and risks should be re-evaluated, and patients should be informed of the risk of pigmentation with long term treatment.

A comprehensive ophthalmological examination (including visual acuity test, slit-lamp examination, and dilated fundoscopy) should be performed at treatment start and at least every 6 months thereafter while treatment is ongoing. Patients already treated with retigabine should have an appointment scheduled for an ophthalmological examination.

If retinal pigment or vision changes are detected, treatment with Trobalt should only be continued after a careful re-assessment of the balance of benefits and risks. Also in patients who develop discolouration of the nails, lips or skin, treatment with Trobalt® should only be continued after a careful re-assessment of the balance of benefits and risks.

Further information on the safety concern

Trobalt® (retigabine) is now indicated as adjunctive treatment of drug-resistant partial onset seizures with or without secondary generalisation in patients aged 18 years or older with epilepsy, where other appropriate drug combinations have proved inadequate or have not been tolerated.

Healthcare professionals should continue to report suspected adverse reactions to the <national competent authority contact details> in accordance with the national spontaneous reporting system rules < enter details as relevant>.

Communication Information

Should you have any questions or require additional information please contact < GSK Local Operating companies to include details>

The information contained in this letter has been endorsed by the European Medicines Agency and national Competent Authorities.

Annexes

Yours sincerely
